4.2 Randomization and Blinding

In this trial, a central random system is used for randomization, subjects will be randomized by an interactive web response system (IWRS) automatically according to grouping sequences to reduce study bias caused by sampling error. The random table is generated by an independent statistician or designated personnel, which is generated by the SAS software based on the number of seeds and blocks pre-set. A block randomization design stratified by sites is adopted. Subject information will be entered by the investigators into the IWRS after verification of inclusion/exclusion criteria. After all subjects undergo Hexvix administration for one hour and then undergo a white light cystoscopy inspection including mapping of the bladder (record lesion number, size and location), subjects will be automatically randomized by the system and grouping information will be feedback to the investigators whether the investigator should continue with a blue light inspection, mapping (record the lesion number, size and location) and biopsy/TURBT (in the same procedure) or to stop the procedure and receive standard treatment by clicking the "Randomization" button in the IWRS. Throughout the trial, the investigators will not be able to modify the group information of subjects.

At each center the Investigator will be blinded to the number of subjects not continuing with Hexvix cystoscopy. A number of subjects (how many should not be known by the investigators) will not continue with Hexvix cystoscopy and these subjects will be distributed randomly among all the centers.

For any subject who has completed the randomization but has dropped out of the trial prior to the initiation of treatment will retain their randomization number (the randomization number assigned to the subject will not be reused). In addition, there will be no replacement for subjects who withdraw early from this clinical trial.

At the start of the study, a minimum of four subjects included at each center will be training subjects. These subjects will undergo Hexvix administration and white and blue light cystoscopy and will have the same safety follow up as all the other included, and treated according to hospital routine practice by the investigator. These subjects should not be included in the randomization procedure, and the subjects will receive subject numbers from a separate series of numbers.

4.3 Study Procedure and Stage

Study will be conducted as study procedures and flow chart in this chapter.

4.3.1 Diagnosis and Pre-treatment Evaluation (visit1)

Pre-treatment evaluation at Visit 1 will only be performed after the patient has agreed to participate,

Study Number: YHCT-HEX-B1

has signed and dated the informed consent form. No treatment will be initiated before the informed consent has been given.

Pre-treatment evaluation will be performed according to the inclusion and exclusion criteria, including:

- 1. Patient informed consent.
- 2. Record demography information (gender, age, ethnicity, height, weight, body mass index, and history of allergies, drug abuse, smoking, alcohol abuse, and blood donation), medical history, and surgery history.
- 3. Record medication history.
- 4. Vital signs include: body temperature, sitting blood pressure, heart rate, and breathing rate. Vital signs should be measured when the investigator judges that the subject's condition is stable.
- 5. Physical examination: general conditions, head and neck, lymph nodes, skin, chest, abdomen, musculoskeletal system (including limbs and spine) and nervous system.
- 6. Pregnancy test (only for women of childbearing age): The pregnancy test for women of childbearing age during the screening period must be negative. If the subject has undergone a pregnancy test within 7 days before the administration, visit 2 can no longer perform the test. During the study period, urine pregnancy test can be performed as needed. If the urine pregnancy result is positive, a serum pregnancy test is required to confirm. If it is confirmed positive, the subject needs to withdraw from the test, and the investigator will continue to follow up the subject until the end of the pregnancy.

Note: Women of childbearing age must take effective contraceptive measures during the study period.

- 7. Review the inclusion and exclusion criteria.
- 8. Record complications, adverse events and concomitant medications/procedures.

4.3.2 Treatment (visit2)

Following successful completion of the pre-treatment evaluations, subjects will continue intoVisit 2. Visit 2 should take place within 14 days of Visit 1 and can be combined with Visit 1.

The following examinations will be performed at Visit 2:

- 1. Vital signs include: body temperature, sitting blood pressure, heart rate, and breathing rate. Vital signs should be measured when the investigator judges that the subject's condition is stable. Note: Vital signs should be examined before and after surgery.
- 2. Physical examination: general conditions, head and neck, lymph nodes, skin, chest, abdomen, musculoskeletal system (including limbs and spine) and nervous system.
- 3. Pregnancy test (only for women of childbearing age): If the subject has undergone a pregnancy test within 7 days before the administration, visit 2 can no longer perform the test. During the study period, urine pregnancy test can be performed as needed. If the urine pregnancy result is positive, a serum pregnancy test is required to confirm. If it is confirmed positive, the subject needs to withdraw from the test, and the investigator will continue to follow up the subject until

Study Number: YHCT-HEX-B1

the end of the pregnancy.

Note: Women of childbearing age must take effective contraceptive measures during the study period.

- 4. Assessment of bladder sympotoms before Hexvix instillation.
- 5. Urine cytology before Hexvix instillation.
- 6. Hexvix instillation.
- 7. White light cystoscopy and lesion evaluation/mapping.
- 8. Randomization.
- 9. Randomization out or blue light cystoscopy with lesion evaluation/mapping.
- 10. Biopsy/TURBT/histology.
- 11. Record complication, adverse events and concomitant medications/procedures.

4.3.2.1 Hexvix instillation Cystoscopy Procedure

1) Instillation

All subjects will have a catheter inserted into their bladder to administer Hexvix solution. The bladder should be evacuated before administering the Hexvix solution. A 50 mL volume of Hexvix 8 mM will then be administered through the catheter. The catheter will be removed, and the subject asked to retain the fluid for 1 hour.

At the end of the instillation period, the subject will be given either local or general anesthesia at the discretion of the Investigator, and the bladder will be evacuated after retaining the Hexvix fluid for 1 hour.

Cystoscopy should not be earlier than 60 minutes after Hexvix instillation to allow tumor cells to synthesize sufficient amount of photoactive porphyrin. The cystoscopic examination should start no more than 3 hours after the start of bladder instillation.

Subjects who fail to retain the Hexvix solution for 60 minutes will complete the procedure, however, cystoscopic examination should not be performed before 60 minutes after instillation.

Cytology will be obtained before Hexvix instillation for all patients.

2) Cystoscopy

All subjects will receive bladder instillation with 50 mL Hexvix 8 mM solution for one hour. After bladder evacuation, cystoscopic examination performed on each subject using following procedures:

- 1. Turn on the white light. Inspection of the bladder and mapping of all papillary lesions and flat and suspicious lesions seen under white light, record lesion number, size and location.
- 2. Randomization:
 - a) If the patient is not randomized to undergo blue light mapping, proceed to step 3.
 - b) If the patient is randomized to continue with blue light mapping, or subjects for

Study Number: YHCT-HEX-B1

investigator training procedure, then they will undergo blue light cystoscopy. Turn to the blue light. Inspection of the bladder and mapping of all papillary lesions and flat and suspicious lesions seen under blue light, record lesion number, size and location.

3. All papillary lesions detected will be resected using TURBT and all flat and suspicious lesions detected will be biopsied. The lesions resected and biopsied should be marked and pathologically examined separately. For patients randomized to undergo blue light cystoscopy and for training patients, the completeness of the resection should always be checked under blue light before finalizing the TURBT procedure until it is ensured that all lesions and suspicious areas are completely resected. Both biopsied and resected tissue will be examined by the local pathologist, then evaluated by independent and blinded central pathologists. Central pathology results will be used as reference standard in the study efficacy endpoints.

Registration of lesions on the bladder chart will include presence of lesion, type (papillary, or flat), number of lesions and location (bladder neck anterior, trigone, around ureteric orifice right, around ureteric orifice left, posterior floor, right lateral wall, cranial wall, left lateral wall, dome, anterior bladder wall and bladder neck posterior).

The cystoscopy will be videotaped, and the video will be used as the source data for the cystoscopy procedure. The cystoscopy video recording of all training subjects (at least 4 subjects) per study site will be reviewed by sponsor for site qualification. After sponsor's written approval, the site can start with cystoscopic examination for randomized subjects.

If assigned investigator and / or sub-investigator failed to fulfil the requirements continuously, more training subjects can be requested and reviewed by the sponsor. It needs to be discussed to see if more trainings can be delivered, or tentatively to evaluate if change of investigator is possible

3) Handling and Interpretation of blue light cystoscopy

When using the blue light cystoscopy, there are several points to consider obtaining the best results. Correct handling of the endoscope is important to optimize the results. False fluorescence may appear and correct interpretation of the fluorescing areas is important.

In general, false fluorescence from normal tissue will be weak and diffuse. The endothelium of blood vessels and inflamed areas may show false fluorescence, but fluorescence from neoplastic lesions will be more intense and usually well demarcated. To avoid false fluorescence and get a brighter picture, the endoscope should be held perpendicular and close to the bladder wall. Tangential light will give false fluorescence. Changing of fluorescence intensity when varying the observation angle indicates false fluorescence, as true fluorescence is persistent. A brighter picture will be achieved using a low magnification if a zoom lens is used. Bleeding will reduce the image brightness and good irrigation should be used. Photo bleaching, which is caused by destruction of the photosensitizer and leads to reduced fluorescence intensity, should be kept at a minimum by avoiding unnecessary delay during inspection and mapping of the bladder. Photo bleaching is normally not a problem during inspection and mapping of the bladder, but may be noticed during extensive use of fluorescence-guided resection. However, regeneration of fluorescence may be seen in areas kept 'in the dark' for a few minutes. To minimize photobleaching, the use of white light should be performed under the lowest possible light intensity. Viewing conditions may be altered by the presence of urine, and the bladder should therefore

Study Number: YHCT-HEX-B1

be adequately evacuated before starting the procedure together with proper irrigation during the examination. Please ensure that the bladder is sufficiently distended as a folded bladder wall may result in increased fluorescence

4) Biopsy/TURBT/Histology

Biopsies/TURBT will be obtained as part of the cystoscopic procedures. Perform biopsy and resection of all lesions and suspicious areas seen in blue light and white light. Both biopsied and resected tissue will be examined by the local pathologist, then evaluated by independent and blinded central pathologists. Central pathology results will be used as reference standard in the study efficacy endpoints.

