Patients	1. Gross haematuria. (Note: Gross haematuria is defined as a heavy bladder bleed resulting in marked amounts of blood in the urine, which may visually limit cystoscopy. Where the haematuria is light, the patient should not be excluded, if in the investigator's opinion, rinsing and/or electro-cautery during cystoscopy will alleviate the possible interference with cystoscopy).
	2. Patients who received BCG immunotherapy or intravesical chemotherapy within 6 weeks prior to the procedure.
	3. Porphyria.
	4. Known allergy to hexaminolevulinate hydrochloride or a similar compound.
	5. Pregnancy or breast feeding or patients of child-bearing potential, including men with partners of child-bearing potential, who are unwilling

tudy Number: YF	C1-HEX-B1 V 2.2, Feb 6 th 202
udy Number: YF	after the medication. (Note: Child-bearing potential is defined as women who are ovulating, pre-menopausal or not surgically sterilized. All women of child-bearing potential must document a negative pregnancy test before study inclusion and use adequate contraception during the study). 6. Participation in other clinical studies with investigational drugs/investigational device either concurrently or within the last 30 days prior to the first study cystoscopy. 7. Patient who is the investigator or any sub investigator, research assistant, pharmacist, study coordinator, other staff or relative thereof directly involved in the conduct of the protocol.
	8. Patients that the investigator believed were unlikely to comply with the protocol.
	9. Subjects with contraindications to white light cystoscopy.
Drug / Device	Drug name: Hexvix (hexaminolevulinate hydrochloride, for intravesical solution, for bladder instillation only) as the photosensitizer to use with blue light cystoscopy Active ingredient: Hexaminolevulinate hydrochloride Device: Cystoscopic equipment with necessary filters to allow both standard white light cystoscopy and blue light (wavelength 380–450 nm) fluorescence cystoscopy
Comparative Drug	Not applicable
	Primary Efficacy Endpoint:
	• The proportion of patients with histology-confirmed tumors (Ta, T1, or CIS) who have at least one such tumor found by Hexvix but not by white light cystoscopy.
E.C. acces	Secondary Efficacy Endpoint:
Efficacy Endpoint	• The proportion of patients with one or more CIS lesions detected only by Hexvix blue light cystoscopy not by white light cystoscopy.

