4.1 Study Type and Design Principle

A Prospective, within patient controlled multicenter study.

This study includes 3 regular visits: screening visit(-2w), cystoscopic examination (day 0), safety follow-up(1w). Study design as below:

[figure not shown]

Fig2. Study design

At the start of the study, a minimum of four subjects included at each center will be training subjects. These subjects will receive the Hexvix administration and undergo white and blue light cystoscopy with tumor resection as below. They will receive the same safety follow up as all the other included patients, after completing the safety follow-up for 1 week, the patients will be treated according to hospital's clinical routine by the Investigator. These patients are not part of the efficacy analyses.

To reduce possible bias in assessment of the objectives, a small number of subjects will be randomized to not continue with Hexvix blue light cystoscopy following white light cystoscopy.

Consented, eligible subjects (Visit 1) will be instilled with 50 mL Hexvix 8 mM solution for one hour. After bladder evacuation, the following procedure will be utilized to accomplish the cystoscopic examination of each subject:

1. Turn on the white light. Inspection of the bladder and mapping of all papillary lesions and flat and suspicious lesions seen under white light, record lesion number, size and location.

2. Randomization:

- a) If the patient is not randomized to undergo blue light mapping, proceed to step 3.
- b) If the patient is randomized to continue with blue light mapping, or subjects for investigator training procedure, then they will undergo blue light cystoscopy. Turn to the blue light. Inspection of the bladder and mapping of all papillary lesions and flat and suspicious lesions seen under blue light, record lesion number, size and location.
- 3. All papillary lesions detected will be resected using TURBT and all flat and suspicious lesions detected will be biopsied. The lesions resected and biopsied should be marked and pathologically examined separately. For patients randomized to undergo blue light cystoscopy and for training patients, the completeness of the resection should always be checked under blue light before finalizing the TURBT procedure until it is ensured that all lesions and

Study Number: YHCT-HEX-B1

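### Does the instruction to keep white light at the lowest possible intensity weaken the white light reading that serves as comparator for the primary endpoint?

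*Combined protocol and SAP*

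**What the plan says.** Section 4.3.2.1 sets the order of the examination: instillation, white light mapping, randomization, blue light mapping for those allocated to it, then resection or biopsy. Step 1 reads "Turn on the white light. Inspection of the bladder and mapping of all papillary lesions and flat and suspicious lesions seen under white light". Section 4.1 repeats it and adds what must be recorded: "mapping of all papillary lesions and flat and suspicious lesions seen under white light, record lesion number, size and location".

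Part 3 of section 4.3.2.1 concerns handling and interpretation of blue light cystoscopy. It opens with "When using the blue light cystoscopy, there are several points to consider obtaining the best results". On bleaching of the photosensitizer it makes these points, in this order:

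- the examiner is to limit bleaching by not letting the inspection drag on;
- "Photo bleaching is normally not a problem during inspection and mapping of the bladder", though it may be seen when fluorescence is used at length to guide resection;
- fluorescence can recover in areas left unlit for a few minutes;
- "To minimize photobleaching, the use of white light should be performed under the lowest possible light intensity".

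The Drug / Device row of the synopsis describes "Cystoscopic equipment with necessary filters to allow both standard white light cystoscopy and blue light" examination. No sentence sets a brightness or image-quality standard for step 1, and none says whether the intensity instruction applies to it.

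**The concern.** The instruction is unrestricted, and step 1 is the only listed use of white light before the blue light map. Taken literally, a site that wants to protect fluorescence could turn the white light down during step 1.

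The primary endpoint (section 7.1) counts a patient when Hexvix finds a confirmed Ta, T1 or CIS tumor that white light did not. The proportion is tested against a fixed 10% in a single group (sections 10.2 and 10.4.2.1). A tumor lost to a dim white light view and then found under blue light would count as a success. The error would run in Hexvix's favour, and no concurrent control would absorb it. The secondary endpoints on CIS and on detection by lesion type use the same white light reading. Sites that understood the sentence differently would add variation between centers.

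**Working it through.** **The test whose integrity is in question.** Inputs from section 10.2: n = 94, null proportion 0.10, alternative 0.20, one-sided level 0.025, exact binomial test.

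- The critical value is the smallest r with P(X ≥ r | n = 94, p = 0.10) ≤ 0.025. P(X ≥ 15) = 0.0465 is too large and P(X ≥ 16) = 0.0239 is small enough, so r = 16.
- Power is P(X ≥ 16 | n = 94, p = 0.20) = 0.8006.

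The plan's 94 patients and 80% power are reproduced.

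**What a shift would do, if there were one.** Suppose dimming added s to the true proportion p. The chance of success becomes P(X ≥ 16 | 94, p + s). The documents give no value for s, so every s below is an assumption.

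| True p | Assumed s | p + s | Chance of success |
|---|---|---|---|
| 0.10 | 0 | 0.10 | 0.0239 |
| 0.10 | 0.01 | 0.11 | 0.0508 |
| 0.10 | 0.02 | 0.12 | 0.0943 |
| 0.08 | 0 | 0.08 | 0.0031 |
| 0.08 | 0.01 | 0.09 | 0.0096 |

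The table shows that the test is sensitive to a biased comparator when the true proportion lies close to 10%. It gives no evidence that s differs from zero. That depends on how the instruction would be followed, which is a matter of reading the text.

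**The texts side by side.**

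1. *Place and purpose.* The sentence closes a run of advice on bleaching within the part on blue light. At mapping, the stated remedy is to avoid delay, and bleaching there is said not to be a usual problem. The stage at which the text expects it to be noticed is resection.
2. *Other uses of white light.* Section 5.2 says that a user ordinarily changes between the two light modes several times in one procedure. Step 3 of section 4.3.2.1 requires a final blue light check that resection is complete. White light used between the blue light map and that check could bleach fluorescence. The instruction therefore has a purpose even if step 1 is left out of it.
3. *The task at step 1.* The investigator must map all papillary, flat and suspicious lesions visible under white light and record number, size and location. For a prescribed task, the lowest possible intensity ordinarily means the lowest at which the task can still be done.
4. *What the investigator knows at step 1.* Under section 4.2, allocation is revealed only after the white light map is complete, and the number of patients who will not go on to blue light is concealed. For any patient, the white light map may be the only guide to resection. This is a strong reason not to work with a poor image.
5. *Viewing conditions elsewhere.* Exclusion criterion 1 removes patients whose bleeding may limit the view. Part 3 asks for evacuation, irrigation and distension. None of this concerns brightness, but it shows that the protocol expects an adequate view.
6. *Record and oversight.* "The cystoscopy will be videotaped, and the video will be used as the source data for the cystoscopy procedure". The sponsor reviews the videos of at least four training patients per site and must approve the site in writing before randomized patients are examined.

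**The case for a change.** The strongest case for a change is that a plausible narrow reading is not a stated scope. The same paragraph does link bleaching to inspection and mapping, so a careful site could apply the instruction at step 1 in good faith. Randomizing some patients out of blue light discourages careless white light inspection, but it cannot offset an instruction followed for everyone before allocation; those randomized out are not in the mFAS either. The requirements used in the training video review are not set out in the protocol, so one cannot tell whether they cover the white light image. One sentence would settle the matter at almost no cost.

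Much of this stands. The scope is unstated, and no sentence guarantees the quality of step 1. It does not follow that the comparator would suffer. To dim step 1 until lesions are missed, an investigator would have to put a general remark about bleaching above the explicit duty to map every visible lesion, for a patient who might receive no blue light.

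Two supporting arguments are weaker than they look. It cannot be asserted that over-dimming would escape the mPPS exclusions: section 10.3.3.2 removes patients whose deviations affected evaluation of the primary endpoint, and failure to carry out step 1 properly could be judged such a deviation. Nor is the instruction one-sided in purpose. Bleaching before or during blue light inspection would lower Hexvix detection, so limiting it protects the index test from the opposite bias.

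**Conclusion.** The sentence is loosely scoped, but it is not a flaw in the design or the analysis. Its position, the remark that bleaching is normally not an issue at mapping, the repeated changes of light mode, the step 1 mapping duty and the concealed allocation all favour a reading in which step 1 remains a standard white light inspection.

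No size can be given. The documents contain nothing that links light intensity to detection, and the probabilities for assumed shifts only illustrate how the test behaves. Sample size, significance level, critical value and analysis sets are unaffected.

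The conclusion assumes that investigators take the instruction to mean the lowest intensity at which the required mapping can be done. If that were doubted, the recorded procedures would allow step 1 image quality to be examined. A sentence stating the scope would be harmless, but it would only write down what competent investigators would already do, so no change to the plan is called for.
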